11.4.2.2 Analyses of secondary efficacy endpoints

The score of the SAQ-Physical Limitation scale will be derived according to the SAQ scoring instructions.

Assuming that the change from baseline to Week 4 in SAQ-Physical Limitation score distribution is normal, a similar model as primary analysis will be fitted. The interaction factors will be explored. The final model will provide adjusted least-squares means (LS means) estimates of the change from baseline to Week 4 in both treatment groups with their corresponding 95% confidence intervals (CIs). The difference of these estimates will be tested at the 1-sided 10% level using an appropriate contrast statement and the 95% confidence interval of the difference will be provided.

In this analysis, the mITT population is considered and the Week 4 assessments will be used regardless of whether the patient has previously discontinued the treatment.

11.4.2.3 Multiplicity considerations

Results of secondary analysis are considered informative ONLY if the primary analysis is positive, therefore the study overall type I error does not need to be adjusted for multiplicity.

For secondary and exploratory efficacy endpoints, p-values will be provided for descriptive purpose only.

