	
Analysis of the key secondary endpoint:
 
The secondary analysis will use a similar model as primary analysis applied to the change from baseline to Week 4 in SAQ PL. The final model will provide adjusted least-squares means (LS means) estimates of the change from baseline to Week 4 in both treatment groups and their corresponding 95% confidence intervals. The difference of these estimates will be tested at the 10% 1-sided alpha level and the 95% confidence interval of the difference will be provided.
 
A safety review with a DMC meeting will start as soon as the first 19 patients will have been randomized and have finished the first week of treatment. Additional analyses for safety may be performed in this study.
 
Safety analysis:
 
Safety analyses will be descriptive, based on the safety population with a focus on BP, creatinine and cystatin C.
 
The safety analysis will focus on the TEAE period. This period is defined as the time from the first administration of the IMP to the last administration of the IMP +5 times the half-life. The half-life being from 20 to 31 hours depending on the age of the patients, a conservative estimate of 31 hours is used for all patients (thus 5 times the half-life corresponds to 5 times 31 hours ie, approximately 7 days).
 
Pharmacokinetic analysis:
 
Descriptive statistics will be provided by SAR407899 dose and time-point for observed concentrations.
 
Pharmacokinetic/pharmacodynamic analysis:
 
Scatter plots of concentrations versus primary/secondary endpoints will be provided. If relevant, some models will be provided to fit the relationship between concentrations and endpoint(s).

DURATION OF STUDY PERIOD (per patient)
	
 • Screening: up to 4 weeks before the first dosing (Day -28 to Day -1) and up to 6 weeks in patients diagnosed with MVA and stable angina without previous PCI who did not have a coronary artery angiography or CCTA in the previous 24 months but between 24 months and 5 years prior to screening and requiring CCTA in this screening period. • Titration phase: 3 weeks. • Maintenance phase: 1 week. • Total duration of treatment: 4 weeks (including titration). • Follow-up: 1 week. • Total study duration: 9 weeks (+/- 2 days) and up to 11 weeks (+/- 2 days) in patients requiring CCTA in screening period.

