11.4.2 Analyses of efficacy endpoints

11.4.2.1 Analysis of primary efficacy endpoint

Model assumptions for normality will be explored prior to the analysis testing.

Assuming that the change in CFR from baseline to Week 4 distribution is normal, an analysis of covariance (ANCOVA) model including the two following fixed categorical effect: treatment group (pooled SAR407899 doses versus placebo) and the presence of angiographically successful PCI (YES/NO) as well as a continuous fixed covariate of baseline CFR will be fitted. The interaction factors will be explored. The final model will provide adjusted least-squares means (LS means) estimates of the change from baseline to Week 4 in both treatment groups with their corresponding 95% confidence intervals (CIs). The difference of these estimates will be tested at the 1-sided 5% level using an appropriate contrast statement and the 95% confidence interval of the difference will be provided.

Let μ_0 and μ_1 be the population means of the change from baseline to Week 4 in CFR under placebo and SAR407899, respectively. The null hypothesis that will be tested is:

$H_0: \mu_0 = \mu_1$ versus $H_1: \mu_0 \neq \mu_1$.

Robustness of this statistical method will be assessed via sensitivity analyses detailed in the Statistical Analysis Plan (SAP), including different methodologies for missing data (multiple imputation and potentially pattern mixture modeling).

In this primary analysis, the mITT population is considered and the Week 4 assessments will be used regardless of whether the patient has previously discontinued the treatment.

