## **1.2 MODIFICATIONS FROM THE STATISTICAL SECTION OF THE PROTOCOL**

At the time of the early study termination decided by the sponsor, only 10 patients were randomized in the study, and only 8 patients have a post baseline CFR assessed (primary efficacy endpoint) . The number of patients initially planned to be randomized in the study was 78, therefore with such few patients finally enrolled in the study, no formal statistical analysis will be performed. The analysis will be only descriptive, with few summary tables and some additional listings.

The following table gives the changes to the protocol statistical section.

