**Table 1 – Statistical analysis changes**

Protocol version	Section number	Description of statistical changes
Amended no 03	11.4.1.2 Compliance	No summary table on compliance will be done. Instead listing with individual treatment intake, and compliance by visits interval will be provided.
	11.4.2.1 Analysis of primary efficacy endpoint	No model will be built. Only descriptive table and listing with information on the uncorrected global CRF will be provided
	11.4.2.2 Analysis of secondary efficacy endpoint	No model will be built for the SAQ-PL. Only descriptive table and listing will be provided
	11.4.2.3 Multiplicity considerations	Not applicable. All results presented are considered informative only.
	11.4.3.1 Adverse events	Incidence tables will be provided as planned. Only one listing will be provided for the treatment emergent adverse events with flag to identify SAE, TEAE leading to treatment discontinuation, AESI.
	11.4.3.2 Laboratory data	No summary statistics will be provided since only local laboratory data are retrieved in this study. Only the incidence of PCSA will be provided, as well as standard listings of patients with PCSAs
	11.4.3.4 Vital signs data	No summary statistics will be provided. Only the incidence of PCSA will be provided, as well as standard listings. In addition Individual graphs for SBP and HR could be provided if necessary
	11.4.3.5 Electrocardiogram data	No summary statistics will be provided. Only the incidence of PCSA will be provided, as well as standard listings
	11.4.4 Analysis of pharmacokinetic and pharmacodynamic variables	No PK nor PK/PD analysis will be performed

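### Does the one-sided 10% test of SAQ-PL undermine the protocol's statement that no multiplicity adjustment is needed?

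*Protocol*

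**What the plan says.** Three parts of the protocol bear on SAQ-PL.

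- **Test level.** The synopsis, under the key secondary endpoint, says: "The difference of these estimates will be tested at the 10% 1-sided alpha level". Section 11.4.2.2 repeats this: "tested at the 1-sided 10% level using an appropriate contrast statement". The primary endpoint, CFR, is "tested at the 1-sided 5% level using an appropriate contrast statement" (11.4.2.1).
- **Gate.** Section 11.4.2.3 treats secondary results as informative only if the primary analysis is positive, and concludes: "therefore the study overall type I error does not need to be adjusted for multiplicity".
- **Status of the p-value.** The next sentence of 11.4.2.3 says that for secondary and exploratory endpoints "p-values will be provided for descriptive purpose only".

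The SAP was written after the sponsor stopped the study with 10 of the planned 78 patients randomized. Section 1.2 states that "no formal statistical analysis will be performed". SAP Table 1 drops the SAQ-PL model and replaces the multiplicity section with: "Not applicable. All results presented are considered informative only".

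**The concern.** A prespecified rejection level implies a decision, and a descriptive p-value implies none. Read side by side, the sections leave the status of SAQ-PL open. If it is descriptive, the 10% level does little work. If it is formally tested, the argument in 11.4.2.3 looks incomplete, because a fixed sequence holds the error at 5% only when every step is tested at 5% or less, and here the second step is at 10%.

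At stake would be a trial with a positive CFR result and an SAQ-PL one-sided p-value between 0.05 and 0.10. One section could be cited to call that result positive and another to call it descriptive, and the choice would be made with the data in hand.

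**Working it through.** **Inputs.** CFR is tested at one-sided 5% (11.4.2.1) and SAQ-PL at one-sided 10% (synopsis, 11.4.2.2). From 11.1: 35 evaluable patients per arm, difference 0.35, SD at baseline 0.65, correlation 0.6 between visits, power 80%. The documents do not give the correlation between the CFR and SAQ-PL test statistics, so it is varied here as an assumption.

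**1. The plan's own figure.** SD of change = 0.65 × √(2 × (1 − 0.6)) = 0.581, which the protocol rounds to 0.58. By the noncentral t distribution at one-sided 5%, power is 79.3% with 34 per arm and 80.4% with 35. The stated 35 per arm is reproduced. Allowing for 10% inevaluable, 35 / 0.9 = 38.9, so 39 per arm and 78 in total.

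**2. Both nulls true.** An SAQ-PL claim first needs a false CFR claim, so P(any false claim) = P(Z₁ > 1.645) = 5.0% at any correlation.

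**3. CFR responds, SAQ-PL does not.** Let Z₁ have mean 1.645 + 0.842 (80% power) and Z₂ have mean 0, jointly normal. The false SAQ-PL rate is P(Z₁ > 1.645 and Z₂ > 1.282). With independent statistics this is 0.80 × 0.10 = 8.0%.

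| Assumed correlation | SAQ-PL at 10% | SAQ-PL at 5% |
|---|---|---|
| −0.3 | 6.3% | 3.0% |
| 0 | 8.0% | 4.0% |
| 0.3 | 9.2% | 4.7% |
| 0.6 | 9.9% | 5.0% |
| upper bound | 10% | 5% |

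The bound follows because the joint probability cannot exceed P(Z₂ > 1.282) = 10%. With independent statistics and CFR power of 50%, 90% or 95%, the rate at the 10% level is 5.0%, 9.0% or 9.5%.

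**4. The disputed band.** With independent statistics, SAQ-PL p-values between 0.05 and 0.10 contribute 8.0% − 4.0% = 4.0 percentage points. The most they can contribute is 10% − 5% = 5 points.

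**5. Cost of tightening to 5%.** A secondary test with 80% power at one-sided 10% has power Φ(1.282 + 0.842 − 1.645) = Φ(0.479) = 68% at one-sided 5%.

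**6. Reading the sections together.** The gate bounds the false-claim rate at 5% for CFR and 10% for SAQ-PL, which are the two levels the protocol assigns. The type I error sentence in 11.4.2.3 gives no numerical study-wise level that this would breach. The texts also allow a coherent combined reading: 10% is a nominal threshold for supportive evidence, considered only after a positive primary and carrying no confirmatory claim.

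**The case for a change.** The strongest case for acting is that the mismatch is explicit and repeated. The synopsis and 11.4.2.2 both set the 10% test, nothing gives 11.4.2.3 precedence, and SAQ-PL is the only secondary efficacy endpoint. Anyone who takes the primary's 5% as the study level can show that the gate does not deliver it: the false SAQ-PL rate is 8.0% with independent statistics and can reach 10%. Aligning the wording would cost nothing. The SAP's change followed from early termination, so it did not settle how the full 78-patient analysis would have been read.

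Part of this stands. The wording is inconsistent, and the arithmetic is right for a formal test judged against 5%. But the 5% benchmark is brought in from outside: the protocol sets it for CFR, not for the study as a whole. A gate and a formal secondary test are compatible, and accepting 10% on a secondary endpoint is a defensible preference in a Phase 2a study. Labelling SAQ-PL descriptive would repeat what 11.4.2.3 already says. Testing it at 5% would give up power for control that the plan does not promise, and would still leave the descriptive sentence to be rewritten.

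**Conclusion.** The concern identifies a wording slip, not an error in the design, and no change follows. The 10% level in the synopsis and 11.4.2.2 fits awkwardly with the descriptive label in 11.4.2.3. The statement that no adjustment is needed holds if SAQ-PL is descriptive, in which case the error is the primary's 5%. It also holds if SAQ-PL is tested at its own 10% level behind the gate. It fails only against a study-wise 5% that the protocol does not state.

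In that last case the excess is bounded at 5 percentage points. At 80% CFR power it is 3.0 points with independent statistics (8.0% − 5%), and 1.3 to 4.2 points at assumed correlations of −0.3 to 0.3. These figures rest on a bivariate normal approximation, a true CFR effect of the planned size and no SAQ-PL effect.

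The point also has no practical consequence. Under the SAP there is no SAQ-PL model and no formal test, so no SAQ-PL p-value can fall in the disputed band and no reported conclusion turns on which section is followed.

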11.4.3 Analyses of safety data

The summary of safety results will be presented by treatment group on the basis of the safety population.

All safety analyses will be performed on the safety population using the following common rules:

- The baseline value is defined generally as the last available value before randomization.
- The analysis of the safety variables will be essentially descriptive and no hypothesis testing is planned.

The following definitions will be applied to laboratory parameters, vital signs and ECG.

- The potentially clinically significant abnormality (PCSA) values are defined as abnormal values considered medically important by the Sponsor according to predefined criteria/thresholds based on literature review and defined by the Sponsor for clinical laboratory tests, vital signs, and ECG.

PCSA criteria will determine which patients had at least 1 PCSA during the TEAE period, taking into account all evaluations performed during the TEAE period, including unscheduled or repeated evaluations. The number of all such patients will be the numerator for the PCSA percentage.

Observation period

- The TEAE observation period is defined as the time from the first dose of IMP up to 7 days after the last dose of IMP.
- The on-study period is defined as the time from randomization until the end of the study (see definition in [Section 6.2.1](#)).

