- c Concomitant medication (if those are not allowed during the study, see exclusion criterion 3 in [Section 7.2.1](#)) needs to be stopped 1 week before baseline CFR assessed by PET scan and during the whole study.
- d Capsules in the morning and at bedtime. If PET assessment on Day 29 no administration at bedtime. If PET assessment delayed, last IMP administration should be done in the morning of the PET assessment.
- e Vital signs: BP & heart rate measurements including search of hypotension (orthostatic or not).
- f Before morning administration, vital signs should be assessed by the investigator or designee except on Day 1 which requires before morning administration, at T1H and T3H. For any safety reasons additional physical examination, vital signs, ECG may be performed at the investigator's discretion.
- g At Day 1 & Day 29 PET assessments, continuous monitoring of heart rate, BP and ECG should be performed throughout the stressor infusion.
- h Restriction rules for CFR assessed by vasodilator stress PET scan (detailed in [Section 10.1.2](#) and [Section 10.1.4](#)) to follow.
- i On Day 1 (or, if not otherwise possible, up to 14 days prior to Day 1) CFR assessed by vasodilator stress PET scan should be performed before the IMP administration. On Day 29 or up to 2 days after (if not otherwise possible) CFR assessed by vasodilator stress PET scan should be performed approximately 1 to 2 hours after morning IMP intake. Prior to baseline PET assessment (on day 1 or up to 14 days prior to day 1), the eligibility criteria must be carefully reviewed (including review of the screening labs), and if the patient no longer qualifies for the study, then he/she should not undergo the PET assessment.
- j To be completed before any other assessment and without any help.

- k Health care resources will include number of out-patients visits by type physician (specialists, general practitioner, other) and impact on working status.
- l Two PK samplings on Day 1 (1h and 3 h post-dose), one PK sampling (pre-dose) at Day 8, Day 15 and Day 22, two PK samplings on Day 29 (pre-dose and 1-3 hours post-dose). The patient will have to come at the site without having taken his morning dose of IMP if the visit occurs in the morning.
- m Only in post-menopausal female patient not receiving hormone replacement therapy.
- n Except hematology.
- o To assign patient number.
- p To obtain the treatment number after specifying the chosen titration.

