9.1.4.1.2 Risks and discomforts from the PET scans

The risks and discomforts to the patients associated with the PET scan include those associated with administration of the vasodilator and potentially aminophylline that may be utilized to reverse the side effects due to vasodilator administration. Also, there are radiation risks related to the procedure and the radioactive flow tracers. These risks are detailed in the patient consent form.

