The patient arrives to the clinical site in the morning on Day 29 (or up to 2 days after at the latest) and should be in fasting state (at least 4 hours) and well hydrated and should avoid, in the following timely manner (whenever possible), the intake of as it relates to the PET assessment:

- 24 hours before CFR assessment :
 - Anti-hypertensive drugs,
 - Beta blockers,
 - Calcium channel blockers,
 - Methylxanthines including caffeinated coffee, tea or other caffeinated beverages, caffeine-containing drug products.
- At least 4 hours before CFR assessment :
 - Nicotine,

- Short acting nitrate.

IMP administration should be continued until the visit to the site.

The following assessments have to be performed:

- Quality of life questionnaires should be filled in prior any other assessment and without any help:
 - Seattle Angina Questionnaire,
 - Patients' perceptions of treatment and symptoms.
- Physical examination (including smoking habits).
- Patient diary collection.
- Body weight.
- Body temperature.
- Vital signs including search of orthostatic BP measurements and resting 12 lead-ECG.
- Blood sampling for renal function (blood creatinine and cystatin C).
- Blood sampling for hematology, biochemistry.
- Collection of urine for urinalysis.
- Collection of PK samples (pre-dose).
- AEs collection.
- Collection of information about any concomitant medications.

After IMP intake:

- Coronary flow reserve assessed by vasodilator stress PET scan with NIMPs administration, is performed approximately 1 to 2 hours after IMP intake.
- Collection of PK samples (1-3h post-dose).
- Call IVRS/IWRS to declare the end of treatment for this patient, except if patient has delay in end-of-treatment PET scan.

If no clinically relevant findings have been detected from all safety examinations until then, the patient can be discharged from the unit in the evening or earlier depending of the investigator's judgment.

Approximately seven days after the last study drug intake, the investigator will prescribe if needed anti-anginal drugs (ie, nitrates) and/or PDE 5 inhibitor.

Only if PET scan performed after Day 29 visit, at home, the patient will take the IMP twice a day (morning and bedtime) and will report on his patient diary IMP information and the angina episodes that will occur and short-acting nitroglycerin intakes.

In case of early IMP discontinuation:

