- Within the first 2 weeks of study treatment patients are to be assessed as soon as possible after study drug stop, using the procedures (except PET scan) planned for the D29/end of treatment visit, including a pharmacokinetic sample (to be collected no later than 3 days after the last study drug intake).
- With at least 2 weeks of study treatment patients are to be assessed as soon as possible after study drug stop, using the procedures planned for the D29/end of treatment visit, including a pharmacokinetic sample (to be collected no later than 3 days after the last study drug intake). PET scan can be performed up to 3 days after study drug discontinuation.

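### The end-of-treatment vasodilator stress test falls inside the TEAE period, and no planned table or listing separates hypotension that it causes from hypotension on study drug alone

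*Protocol*

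**What the plan says.** Protocol 11.4.3 (Observation period) defines the TEAE period as the "time from the first dose of IMP up to 7 days after the last dose of IMP". The clinical trial summary gives the basis of the 7-day tail: "thus 5 times the half-life corresponds to 5 times 31 hours ie, approximately 7 days".

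On the end-of-treatment stress test, Protocol 10.1.4 says: "Coronary flow reserve assessed by vasodilator stress PET scan with NIMPs administration, is performed approximately 1 to 2 hours after IMP intake". For patients who stop early after at least 2 weeks of treatment, the same section says: "PET scan can be performed up to 3 days after study drug discontinuation". Those who stop within the first 2 weeks have no end-of-treatment scan. At baseline, note i to the flow chart in Protocol 1.3.1 says: "CFR assessed by vasodilator stress PET scan should be performed before the IMP administration".

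Protocol 9.1.4.1.1 has heart rate, blood pressure and ECG recorded during the stressor and in recovery. Protocol 9.1.4.1.2 expects side effects and mentions "aminophylline that may be utilized to reverse the side effects due to vasodilator administration".

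Protocol 10.4.1.3 makes an SBP below 90 mmHg an AESI, symptomatic or not. Protocol 10.4.3 requires a vital-sign abnormality to be recorded as an adverse event if it is defined as an AESI. It also asks for onset date and for causality to the IMP, the NIMP or a study procedure.

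Protocol 11.4.3.1 tabulates AESIs by category and preferred term within treatment group. SAP Table 1 keeps the incidence tables and reduces the listings: "Only one listing will be provided for the treatment emergent adverse events with flag to identify SAE, TEAE leading to treatment discontinuation, AESI". For potentially clinically significant abnormalities (PCSAs), Protocol 11.4.3 counts patients "taking into account all evaluations performed during the TEAE period, including unscheduled or repeated evaluations".

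**The concern.** Hypotension and orthostatic hypotension are the risks named in the safety objective (Protocol 5.2). Apart from patients who stop early or miss the scan, everyone receives a second vasodilator within the period over which those events are counted. A qualifying fall in pressure during the infusion enters the same row of the same table as a fall on study drug at home. The reported rate then answers a mixed question: how often pressure fell on study drug, or on study drug plus a stressor. If the stressor often causes such falls, both arms show high rates and the contrast between them looks smaller than the drug's own effect. A reader of the planned outputs could not undo this, because neither the tables nor the listing flags say which events belong to the stress session.

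**Working it through.** **The plan's own figure.** The tail is 5 × 31 h = 155 h, and 155 / 24 = 6.46 days. Rounded up this gives the stated 7 days.

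**Where each stress test falls.**
- Baseline scan: before the first dose, so outside the TEAE period.
- Day 29 scan, or up to Day 31: dosing continues until the scan, which follows the morning dose by about 1 to 2 hours, so inside.
- Scan after an early stop with at least 2 weeks of treatment: up to 3 days after stopping, and 3 < 7, so inside.

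**How a stressor event reaches the AESI table.** SBP below 90 mmHg during the infusion meets the AESI definition (10.4.1.3). It must therefore be recorded as an adverse event (10.4.3). Its onset lies in the TEAE period (11.4.3), so it counts in the AESI table (11.4.3.1). No step removes it.

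**Size, by assumption.** The documents give no event rates for drug or stressor. Let p be an arm's risk of a hypotension AESI apart from the stress session, and s an independent stressor risk equal in both arms. Then

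reported risk = 1 − (1 − p)(1 − s),

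and the difference between arms is (1 − s) × (p_active − p_placebo).

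With p = 20% on active and 5% on placebo (assumed):

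| s | Active | Placebo | Difference (points) | Ratio |
|---|---|---|---|---|
| 0% | 20.0% | 5.0% | 15.0 | 4.0 |
| 10% | 28.0% | 14.5% | 13.5 | 1.9 |
| 20% | 36.0% | 24.0% | 12.0 | 1.5 |
| 30% | 44.0% | 33.5% | 10.5 | 1.3 |
| 50% | 60.0% | 52.5% | 7.5 | 1.1 |

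For s = 10%: active 1 − 0.80 × 0.90 = 0.280; placebo 1 − 0.95 × 0.90 = 0.145; difference 0.90 × 15 = 13.5 points; ratio 0.280 / 0.145 = 1.93.

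Other assumed starting rates behave the same way. With 25% versus 10% and s = 10%, the rates become 32.5% and 19.0% (difference 15 to 13.5 points, ratio 2.5 to 1.7). With 30% versus 5%, they become 37.0% and 14.5% (25 to 22.5 points, ratio 6.0 to 2.6).

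The difference is fairly robust to s. The ratio moves towards 1 much faster, because the placebo rate starts low.

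**The case against.** Much of the case on the other side stands.

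- **The information is not lost.** Causality to NIMP or procedure is recorded for every adverse event. The gap is in the outputs only.
- **Placebo has the same stress test.** With an equal stressor effect the result is dilution, not a spurious drug effect. The near-vanishing ratio of 1.1 appears only at the assumed 50% extreme.
- **Excluding the session outright would cost information.** Scheduled vital signs on Days 8, 15, 22 and 29 are pre-dose (Protocol 9.2.4.3 and 1.5). After Day 1, the stress session is the only scheduled blood pressure monitoring in the hours after a dose. If the drug deepens the fall under the stressor, that is a real drug effect and should stay visible.
- **Practical weight is low.** The SAP (1.2) reports 10 randomized patients, 8 with a post-baseline CFR, so the sessions could almost be read one by one. Even so, the listing does not say which events belong to a session.

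Three stronger readings are tempting, and the documents do not support them.

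- **That dizziness during the stressor counts as an AESI.** The symptom wording in 10.4.1.3 is tied to standing up, and the orthostatic limbs need seated and standing readings. Dizziness during the infusion is an ordinary TEAE unless one of those conditions, or an SBP below 90 mmHg, is met.
- **That infusion readings inflate the vital-sign PCSAs.** SAP 1.3 uses the mean of three sitting measures, and the Day 29 chart schedules vital signs only at arrival. On the other hand, SAP Appendix A applies the SBP criterion to every position except standing, including a missing position, and the SAP's 1-hour window (0.5 to 2 hours after dosing) overlaps the scan. The documents do not say whether infusion readings enter those datasets, so this is an open question.
- **That active patients who stop for hypotension and miss the scan erode the contrast further.** The AESI table counts patients. A patient who stopped on the protocol's hypotension criteria has already met an AESI limb and is already counted. If all who miss the scan are among the 20%, the active rate stays at 0.20 + 0.80s, or 28% at s = 10%, as in the table. Early stops for other reasons could matter, but the documents give no rate or direction for them.

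**Conclusion.** The point holds as a gap in the planned outputs. The stress test lies inside the TEAE period by the protocol's own timing, and an SBP below 90 mmHg caused by the stressor qualifies as a hypotension AESI. No planned table or listing flag sets such events apart, although their causality is recorded.

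The consequence is higher rates in both arms and a risk difference reduced by the factor (1 − s): 15 to 13.5 points, and a ratio from 4.0 to 1.9, at 20% versus 5% with s = 10%. This rests on assumed rates, on independence of the two risks and on equal stressor exposure and effect by arm. It does not show that any observed rate is wrong.

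It is a cheap improvement of low priority, since safety is descriptive with no testing and only 10 patients were randomized. At that size one event still shows: with about 5 patients per arm (assumed), a single stressor event moves a rate by 1/5, or 20 points.

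**What to change.** In SAP 1.3 and Table 1:

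1. Define a PET-stress flag for events with onset between the start of the stressor and the end of recovery monitoring, or judged related to the NIMP or study procedure. Identify flagged events also judged IMP-related. Protocol 10.4.3 asks only for the onset date, so if clock times are not held, state how onset on the scan day is handled.
2. Keep the planned all-TEAE and AESI tables unchanged.
3. Add hypotension AESIs and TEAEs by arm with flagged events excluded.
4. List flagged events by arm, with the number of patients scanned as denominator. Count scans directly; do not infer them from available CFR values.
5. State whether blood pressure, heart rate and ECG readings during the infusion enter the PCSA datasets.

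The cost is one derived flag and one more table, mainly from data already collected. Showing results with and without flagged events keeps any drug–stressor interaction in view, which replacing the main table would not.
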